#### 13.3 Data Analysis

Data analysis of the study will be descriptive in nature. Demographic and clinical characteristics of the sample, toxicity by grade, as well as tumor response, duration of response, and length of follow-up will be summarized using descriptive statistics. Binomial proportions and their 90% confidence intervals will be used to estimate the response rates of therapy. Binomial proportions and their 90% confidence intervals will also be calculated for the efficacy based on immune response criteria (Appendix D). The Kaplan-Meier method will be used to evaluate the response duration. Analysis of variance methods will be used to evaluate the effects of treatment and time on the viral load measurements, as well as measurements of viral transcripts. The incidence of toxicities will be estimated using the binomial proportion and its 90% confidence interval. A proportional hazards analysis with viral load measures as time dependent covariates will be used to evaluate the effects of treatment and structure the effects of these measures on duration of response. Detailed analysis of correlative studies and biomarkers are listed in Section 9.

The safety and tolerability will be monitored every 2 weeks. All patients who receive treatment with nivolumab will be eligible for safety and tolerability analysis. A Bayesian sequential monitoring method [58] will be used for safety analysis and the stopping rule is defined as  $Pr(\theta>0.10 | data)>0.90$ , where  $\theta$  denotes the proportion of patients who discontinue therapy due to intolerable toxicity. That is, enrollment will be stopped early whenever, given the accumulated observed data, there is >90% probability that the discontinuation of therapy is greater than 10%. Specifically, enrollment will be stopped early if 3 patients discontinue therapy in the first 12 patients, or 4 patients discontinue therapy in the first 19 patients, or 5 patients discontinue therapy before the last patient enrolled. These boundaries were obtained using the free-download software Multc99 (version 2.1) from M.D. Anderson Cancer Center. We assume that the parameter  $\theta$ follows a prior distribution of beta ( $\alpha$ ,  $\beta$ ), with  $\alpha$  and  $\beta$  representing the number of patients discontinuing and continuing therapy respectively.

	Ethnic Categories				T ( )
Racial Categories	Not Hispanic or Latino		Hispanic or Latino		Total
	Female	Male	Female	Male	
American Indian/ Alaska Native	0	0	0	0	0

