#### 13.2 Study Design

At least 20 evaluable patients will be enrolled for this study. Evaluable patients will be those patients who received study medication. The sample size of 20 patients is based on Simon's Optimal 2-stage design, with the assumption that an overall response rate of 40% is the minimum response rate that would be considered for further analysis of this approach, compared to a rate of 10% under null hypothesis. Thus, 20 subjects are required to with a one-side type 1 error rate of 5% and a power of 90%. If 1 or fewer responses are seen among the first 9 subjects enrolled, the trial is stopped early for futility. In contrast, if 2 or more responders are observed out of the 9 patients in the first stage, additional 11 patients will be enrolled in the 2nd stage. In a multicenter study such as this, however, it is difficult for a trial to reach the planned sample exactly. The investigators would not turn away patients who have already been approached for participation just because the number of patients needed has been met. Therefore, we adopted a flexible Phase II design (Chen and Ng 1998) to allow the actual number at final stage to deviate slightly from

what is planned. Due to the expected relatively low accrual rate, we expect that the interim analysis could be performed at the designed sample size. Only the decision boundaries at the 2nd-stage are determined following Chen and Ng's flexible design and programed by the study statistician [57]. That is, if 5 or more responders are observed out of 20-23 patients, or 6 or more responders are observed out of 24-25 patients, we would conclude that preliminary evidence for efficacy exists and that further investigation of the treatment is warranted.

The interim analysis will be based upon independent review of response, with a minimum time frame of 2 months for the interim analysis. Accrual will not be halted during the interim analysis.

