#### **13.4.2** Evaluation of Response

All patients included in the study must be assessed for response to treatment, even if there are major protocol treatment deviations or if they are ineligible. Each patient will be assigned one of the following categories: 1) complete response, 2) partial response, 3) stable disease, 4) progressive disease, 5) early death from malignant disease, 6) early death from toxicity, 7) early death because of other cause, or 8) unknown (not assessable, insufficient data). [Note: By arbitrary convention, category 8 usually designates the "unknown" status of any type of data in a clinical database.]

All of the patients who met the eligibility criteria (with the possible exception of those who received no study medication) should be included in the main analysis of the response rate. Patients in response categories 4-9 should be considered to have a treatment failure (disease progression). Thus, an incorrect treatment schedule or drug administration does not result in exclusion from the analysis of the response rate. Precise definitions for categories 4-9 will be protocol specific.

All conclusions should be based on all eligible patients. Subgroup analyses may then be performed on the basis of a subset of patients, excluding those for whom major protocol deviations have been identified (*e.g.*, early death due to other reasons, early discontinuation of treatment, major protocol violations, etc.). However, these subgroup analyses may not serve as the basis for drawing conclusions concerning treatment efficacy, and the reasons for excluding patients from the analysis should be clearly reported. The 95% confidence intervals should also be provided.

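### The 90% interval for the primary response rate ignores the two-stage design and has no named method; if exact, it includes the 10% null at 5 of 21, 22 or 23, where efficacy is declared

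*Combined protocol and SAP*

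**What the plan says.** Section 13.2 sets the design: "The sample size of 20 patients is based on Simon's Optimal 2-stage design". The null rate is 10% and the target 40%, with a "one-side type 1 error rate of 5% and a power of 90"%. The stage 1 rule is: "If 1 or fewer responses are seen among the first 9 subjects enrolled, the trial is stopped early for futility". The final sample may run from 20 to 25. With at least 5 responders among 20 to 23 patients, or at least 6 among 24 or 25, the protocol states "we would conclude that preliminary evidence for efficacy exists".

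Section 13.3 then plans the estimate: "Binomial proportions and their 90% confidence intervals will be used to estimate the response rates of therapy". It describes the analysis as descriptive, names no interval method and does not mention the interim look. Section 13.4.2 adds, after its subgroup text: "The 95% confidence intervals should also be provided". Nowhere is an interval or estimate adapted to the two stages.

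**The concern.** A trial that can stop at 9 patients does not yield a fixed-sample binomial count. Results with 1 or fewer responses among the first 9 and 5 or more in total cannot occur, yet an ordinary binomial interval counts them. Two things follow. The published interval can include the null rate in a trial that has just declared efficacy by its own rule. And, because the method is unnamed, the choice between an interval that clashes with the rule and one that does not could be made after the result is known. Response is one of the two primary objectives, so readers will compare this interval with 10%.

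**Working it through.** **Inputs (13.2 and 13.3).** p0 = 0.10, p1 = 0.40, one-sided alpha 0.05, power 0.90; n1 = 9, stop at 1 or fewer; success at 5 or more of 20–23 or 6 or more of 24–25; 90% interval.

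**Step 1. Reproduce the design.** A search over two-stage designs for the smallest expected sample size under p0 returns 1/9 then 4/20, with exact alpha 0.0349 and power 0.9018. The stop probability under p0 is 0.9^9 + 9(0.1)(0.9^8) = 0.775. The stated design holds.

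**Step 2. Lower limits at the success boundary.** For s responses among N, the Clopper-Pearson 90% lower limit L solves P(X ≥ s | N, L) = 0.05. It lies below 10% exactly when the single-sample tail at p = 0.10 exceeds 0.05. The stage-ordered limit replaces that tail with the two-stage one, P(X1 ≥ 2 and X1 + X2 ≥ s | L) = 0.05.

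| Result | Single-sample tail at 10% | Exact lower limit | Two-stage tail at 10% | Stage-ordered lower limit |
|---|---|---|---|---|
| 5/20 | 0.043 | 10.4% | 0.0349 | 11.0% |
| 5/21 | 0.052 | 9.9% | 0.0405 | 10.6% |
| 5/22 | 0.062 | 9.4% | 0.0464 | 10.2% |
| 5/23 | 0.073 | 9.0% | 0.0524 | 9.9% |
| 6/24 | 0.028 | 11.5% | 0.0219 | 12.1% |
| 6/25 | 0.033 | 11.0% | 0.0255 | 11.7% |

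The exact interval clashes with the rule at 5/21, 5/22 and 5/23 only. The stage-ordered interval clashes only at 5/23, because the rule there has a type I error of 5.24%.

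Other methods: Wilson lower limits are 12.7%, 12.1%, 11.5%, 11.0%, 13.5% and 13.0% for N = 20 to 25, so no clash. Wald limits are 9.1%, 8.5%, 8.0%, 7.6%, 10.5% and 9.95%, so a clash at every boundary except 6/24.

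**Step 3. How often.** Given that final size, the chance of exactly 5 responses is 13–14% at a true 20%, 9–12% at 30%, and 4.4%, 3.2% and 2.4% (N = 21, 22, 23) at 40%.

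**Step 4. Coverage under the two-stage sampling.** Coverage at p is the total probability of all final outcomes (0 or 1 of 9, or s of N) whose interval contains p.

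- Exact: 96.5%, 96.8%, 90.7%, 96.3% and 94.5% at true rates of 10, 20, 30, 40 and 50% (N = 20). At N = 23 and a true 50% it is 89.5%. On a fine grid from 5% to 70% for N = 20, 23 and 25, the lowest value was 88.4%.
- Wilson, N = 20: 84.5% at 40%, but 91.7% at 20%.
- Wald, N = 20: 60.3%, 83.4%, 72.1% and 84.5% at 10, 20, 30 and 40%.
- Stage-ordered: never below 90% on the same grid.

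**Step 5. Bias of the plain proportion.** Let A = 9p(1−p)^8 and S = (1−p)^9 + A. The expected proportion is A/9 + [(9p − A) + (N − 9)p(1 − S)]/N.

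- p = 0.40, N = 20: A = 0.0605, S = 0.0705; 0.0067 + (3.5395 + 4.0896)/20 = 0.3882. Bias −1.2 points.
- p = 0.20, N = 20: A = 0.3020, S = 0.4362; 0.0336 + (1.4980 + 1.2403)/20 = 0.1705. Bias −3.0 points.
- The largest bias found was −3.4 points (N = 25, p = 0.20).

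Given that stage 2 is reached, the mean is the bracket divided by N(1 − S): 2.7384/(20 × 0.5638) = 24.3% at a true 20%, and 41.0% at a true 40%. Both are too high.

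**Step 6. Unbiased estimate (UMVUE) at 5/20.** Sum over x = 2 to 5: Σ C(8, x−1)C(11, 5−x) / Σ C(9, x)C(11, 5−x) = 3546/12072 = 29.4%, against 25.0% raw. At 5/23 it is 27.9% against 21.7%. At N = 20 its root mean squared error is larger than the raw proportion's at a true 10% (9.7 against 7.6 points) and 20% (12.0 against 11.1), and smaller at 30–40%.

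**The case against.** The best counter-argument is that nothing turns on this interval. The decision rests on prespecified counts, 13.3 calls the analysis descriptive, and 13.2 claims only preliminary evidence. All of that stands. So does the narrowness: with the exact interval, a clash needs exactly 5 responses and an over-run to 21–23, and does not arise at the planned 20.

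Some stronger readings are tempting but not supported.

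- *The planned interval both contradicts the decision and lacks 90% coverage.* The plan names no method. The exact interval can contradict the rule but roughly keeps its level; Wilson under-covers at some rates but never contradicts it. Only Wald does both, and nothing says Wald will be used.
- *The reported rate will be too low.* That is an average over trials that stop at 9. Among trials that continue, it averages too high.
- *The 95% intervals in 13.4.2 prove a two-stage fault, since the exact 95% interval includes 10% at every success boundary.* A one-sided 5% rule corresponds to a 90% interval. The two-stage tails at N = 20 to 23 (0.0349 to 0.0524) all exceed 0.025, so a design-based 95% interval includes 10% there too. The differing levels are a separate matter of consistency.
- *The UMVUE should become the headline.* Its larger error at low true rates makes that a trade-off rather than a correction.

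**Conclusion.** The point holds as a matter of reporting. An unnamed fixed-sample binomial interval is planned for a two-stage trial. If it is the exact one, it includes the 10% null at three results where the protocol declares efficacy, with shortfalls of 0.1, 0.6 and 1.0 percentage points. Bias in the plain proportion is modest: 1.2 points at the 40% target and at most 3.4 points in the settings checked. The error rates of the decision are untouched.

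The figures assume that stage 1 is judged on the first 9 patients, that the final size between 20 and 25 does not depend on the responses, and that the interval is computed at the size reached.

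**What to change.** In 13.3, state that the 90% interval for the primary response rate will be the exact interval based on the stage-wise ordering of the two-stage design, computed at the final sample size reached. Keep the raw proportion as the reported estimate. If the UMVUE is given, label it supplementary and note its larger error at true rates of 10–20%. Say in advance that at 5/23 the interval will still include 10% (lower limit 9.9%), because the rule at that size slightly exceeds 5%. State which confidence level applies to the primary analysis, so that 13.3 and 13.4.2 agree.

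The cost is a sentence or two and a little more analysis work, with no extra data or patients. Upper limits become somewhat higher: 47.8% instead of 45.6% at 5/20, and 45.0% instead of 40.4% at 5/23.

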## SCHEMA

Nivolumab will be given at 240 mg every 2 weeks for 4 initial doses, followed by up to 42 doses if tolerated. Therapy is continued in each individual until sign of tumor progression or intolerable toxicity, or other endpoint is reached.

Imaging will be performed every 12 weeks for individuals with abnormal imaging at study initiation or during the course of the study.

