## 2.1.1 HTLV-1 Associated Adult T-Cell Leukemia Lymphoma

Although HTLV-2 is not clearly associated with a clinical disorder, HTLV-1 is closely associated with two clinical disorders [1]. About 5% of HTLV-1 infected individuals eventually develop a form of myelopathy known as HTLV-1 myelopathy (HAM) or tropical spastic paraparesis (TSP). It is characterized by lower limb spasticity, bowel and bladder disturbances, and slow but steady progression over several years. HTLV-1 has also been associated with other inflammatory clinical conditions, including uveitis, arthropathy, myopathy, pneumopathy, and a Sjogren's disease-like syndrome [8]. Some investigators have suggested that these disorders are related to high virus load, overstimulation of dendritic cells, resulting in chronic production of high levels of type 1 interferons and interferon-stimulated gene expression.

About 5% of HTLV-1 infected individuals develop a T-cell non-Hodgkin's lymphoma designated adult T-cell leukemia lymphoma (ATLL). It occurs almost exclusively in individuals who acquired HTLV-1 as a result of breast feeding, although four or five decades are generally required before development of disease. ATLL is characterized by frequent blood and bone marrow involvement, hypercalcemia, and lytic bone lesions. It is most commonly a CD4+ leukemia/lymphoma, although occasional examples of CD8+ lymphoma have been described. ATLL may fit into a variety of pathological subtypes as classified by the International Working Party Formulation. Clinical classifications of ATLL have included a "smoldering" disorder characterized by rash and minimal blood involvement, as well as a chronic form of ATLL, which have median survivals of two years or more (Fig 1) [9]. In contrast, a "lymphomatous" form of ATLL and an "acute" form of ATLL have median survivals of 3-6 months.

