## 5. TREATMENT PLAN

# 5.1 Agent Administration

Treatment will be administered on an outpatient basis. Reported adverse events and potential risks are described in Section 7. Appropriate dose modifications are described in Section 6. No investigational or commercial agents or therapies other than those described below may be administered with the intent to treat the patient's malignancy.

Regimen Description					
Agent	Premedications; Precautions	Dose	Route	Schedule	Cycle Length
Nivolumab	None	in 100 ml NS	IV over 60 minutes (+/- 10 minutes)	Every 2 weeks	14 days
**Doses as appr	opriate for assigned do	se level.	· · · · ·		

A flat dose of 240 mg will be administered. There will be no dose modifications allowed.

Nivolumab is to be administered as a 60-minute (+/- 10 minutes) IV infusion, using a volumetric pump with a 0.2/1.2 micron in-line filter at the protocol-specified dose. The drug can be diluted with 0.9% normal saline for delivery but the total drug concentration of the solution cannot be

below 1.0 mg/mL. It is not to be administered as an IV push or bolus injection. At the end of the infusion, flush the line with a sufficient quantity of normal saline.

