9.4 Exploratory/Ancillary Correlative Studies

# 9.4.1 HTLV-1 Studies - Biological Markers of Anti-Tumor Response

# A. HTLV-1 DNA Proviral Load

Hypothesis: Nivolumab will enhance anti-ATLL immune responses and result in a decrease in HTLV-1 proviral load.

Rationale: An effective immune response against HTLV-1 should decrease the number of HTLV-1 infected cells.

Preclinical and Clinical Results: See Section 2.1 for HTLV-1 Proviral DNA and Cell-Associated and Virion RNA Load and Protein Expression (2.1.2).

Assay Methodology: Genomic DNA will be extracted from PBMCs isolated from whole blood obtained at baseline, Day 1 of Cycle 3, Day 1 of Cycle 5, every 12 weeks thereafter, and at the end of study time point, and tumor tissue at baseline and end of study time point (if available). The HTLV-1 DNA assay is performed with PBMCs, prepared in a BSL3 facility, measuring the number of copies of integrated or unintegrated viral genome with a Biorad digital drop PCR assay [53]. PCR is performed with tax primers that amplify a 154 bp region, and a FAM/MGB probe. Additionally, in a duplex PCR, a cellular housekeeping gene, ribonuclease P protein subunit P30 is amplified and detected with VIC/MGB probe. DNA will be digested with BamHI, mixed with the primers and probes and Bio-Rad 2× Supermix, and then emulsified using a QX-200 droplet generator, and PCR performed in a 96 well plate, and analyzed on the QX200 droplet reader. QuantaSoftware version 1.3.2.0 is used to quantify the copies/µl. Thresholds are determined manually for each experiment, according to the negative controls, which include a no template control and DNA from a healthy volunteer. Droplet positivity is determined by fluorescence intensity; only droplets above a minimum amplitude threshold are counted as positive. The PVL is calculated as the percentage of infected cells Data normalization is accomplished by applying the log (base 2) transformation, calculating the mean and standard deviation (SD), and defining the lower (mean-2SD) and upper (mean+2SD) values of the expected range for each assay type. These values are used to convert the log transformed values to a percentage of the expected range for each assay type, by subtracting the lower range value for the assay first then dividing by the difference of the upper and lower values of the expected range for the assay. Linear relationship of the postnormalized values is assessed using Pearson correlation.

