# **11. MEASUREMENT OF EFFECT**

# **11.1** Antitumor Effect

For the purposes of this study, patients should be re-evaluated for response every 12 weeks. In

addition to a baseline scan, confirmatory scans should also be obtained 12 weeks following initial documentation of objective response.

Response and progression will be evaluated in this study using criteria suggested by Tsukasaki et al [19].

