#### **13. STATISTICAL CONSIDERATIONS**

#### 13.1 Study Objectives and Endpoints

The primary objective of this study is to determine safety, tolerability, and efficacy of nivolumab for patients with HTLV-associated ATLL. The safety and tolerability will be measured by the frequency of adverse events (AEs) and the number of patients who discontinue therapy due to intolerable toxicity, while the efficacy will be measured as overall response (Complete Response/CR+Partial Response/PR) rate.

The secondary objectives include

- To determine effects of nivolumab on HTLV-1 proviral DNA and RNA loads;
- To determine the effects of nivolumab on anti-HTLV-1 and anti-ATLL immune responses;
- To determine effects of nivolumab on HTLV-1 integration site clonality.

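### Viral load: a single-arm trial gives the planned ANOVA no separate treatment factor, and the plan does not say how repeated samples that end with progression will be analysed

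*Combined protocol and SAP*

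**What the plan says.** The first secondary objective in Section 13.1 is: "To determine effects of nivolumab on HTLV-1 proviral DNA and RNA loads". The only model offered for it is one sentence in Section 13.3: "Analysis of variance methods will be used to evaluate the effects of treatment and time on the viral load measurements", which goes on to cover viral transcripts.

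The rest of the design is as follows.

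- **One arm, one dose.** Section 5.1: "A flat dose of 240 mg will be administered". There is no comparator.
- **Repeated blood samples.** Section 9.4.1 (A) has them "obtained at baseline, Day 1 of Cycle 3, Day 1 of Cycle 5, every 12 weeks thereafter, and at the end of study time point".
- **When sampling stops.** The Schema says: "Therapy is continued in each individual until sign of tumor progression or intolerable toxicity, or other endpoint is reached". The scheduled draws run with treatment and close with an end-of-treatment sample.
- **Response schedule.** Under Section 11.1, "patients should be re-evaluated for response every 12 weeks".

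Section 13.3 refers to Section 9 for detail on the correlative analyses. For viral load, Section 9.4.1 describes the assays, a log base 2 normalisation of DNA load, Pearson correlation, and an aim to relate load to clinical response. The RNA result is a ratio to a housekeeping gene, multiplied by 100 and not logged. I found no patient effect, covariance structure, named contrast, missing-data rule or treatment of the end-of-treatment sample in either section.

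**The concern.** Two things are unsettled. First, an effect of treatment separate from time needs patients or periods that differ in treatment other than through time since baseline, and this design has none between patients.

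Second, ANOVA covers several analyses that behave differently on these data:

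- Applied visit by visit as if samples were independent, it discards the within-patient pairing and overstates the uncertainty of change.
- In the classical repeated-measures form, it keeps only patients with every visit.
- Either of these, at later visits, describes patients who have not yet stopped for progression or toxicity. If rising load accompanies progression, those patients will tend to have the lower loads.

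An apparent fall in load is what Section 9.4.1 hypothesises, so the likely bias runs toward the expected finding. The first secondary objective would then be answered by whichever version is chosen after the data are in.

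**Working it through.** **1. The plan's own figures.** No sample size, SD, correlation or precision is stated for viral load. The only sample-size calculation is the two-stage response design. An exact binomial search at 10% against 40% returns the stated design: 9 + 11 patients, stop at 1 or fewer of 9, success at 5 or more of 20. Its type 1 error is 0.0349 and its power 0.9018. For viral load this only fixes the number of patients at about 20, or 9 if the trial stops at stage 1.

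**2. What is estimable.** A treatment indicator equals 1 for every patient, so it is aliased with the intercept. If it is coded 0 at baseline and 1 afterwards, it is a function of visit and is aliased with categorical time. What remains is change from baseline within patient.

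**3. Draw times.** With 14-day cycles, Cycle 3 Day 1 is week 4 and Cycle 5 Day 1 is week 8, counted from the first dose. The 12-weekly draws follow at weeks 20, 32 and so on. The first scheduled response evaluation, at week 12, falls between the week 8 and week 20 draws.

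**4. Precision of change from baseline** (SD units, complete pairs, equal variances; correlation ρ is assumed).

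- Unpaired SE = √(2/n). Paired SE = √(2(1−ρ)/n). Ratio = √(1/(1−ρ)).
- Half-width of the 95% interval at n = 20, unpaired: 2.024 × √(2/20) = 0.64.

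| ρ | paired half-width, n = 20 | SE ratio |
|---|---|---|
| 0.3 | 0.55 | 1.20 |
| 0.5 | 0.47 | 1.41 |
| 0.7 | 0.36 | 1.83 |
| 0.8 | 0.30 | 2.24 |
| 0.9 | 0.21 | 3.16 |

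At n = 9 the unpaired half-width is 1.00 SD. The paired one runs from 0.91 (ρ = 0.3) to 0.34 (ρ = 0.9).

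**5. How many patients might still be sampled.** The plan gives no dropout rate. As a bracket only, suppose time on treatment were exponential with the survival medians of Section 2.1.1. For the lymphomatous and acute types the text ends "form of ATLL have median survivals of 3-6 months"; for smoldering and chronic disease it says "which have median survivals of two years or more". Expected number of 20 = 20 × 0.5^(months/median), at 4.345 weeks per month.

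| Median | week 4 | week 8 | week 20 | week 32 |
|---|---|---|---|---|
| 3 months | 16.2 | 13.1 | 6.9 | 3.6 |
| 6 months | 18.0 | 16.2 | 11.8 | 8.5 |
| 24 months | 19.5 | 19.0 | 17.5 | 16.2 |

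**6. Direction of selection.** A simulation used draws at weeks 0, 4, 8, 20 and 32, baseline SD 1, ρ = 0.7 apart from slopes, slope SD 0.25 per month, true mean change 0, and dropout more likely the larger the observed rise from baseline. All of these are assumptions. Mean estimated change at week 32, n = 20:

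| Patients left | completers only | visit-by-visit ANOVA | likelihood, missing at random (SD of estimate) |
|---|---|---|---|
| about 14 | −0.38 | −0.30 | 0.01 (0.51) |
| about 10 | −0.71 | −0.56 | −0.02 (0.76) |
| about 6 | −1.02 | −0.80 | −0.14 (1.18) |

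At n = 5,000 the likelihood estimate is 0.00 to −0.01 in the same three settings, while the other two biases persist. The likelihood estimator here left the covariance unstructured, so its near-zero bias is an upper guide to what a simpler mixed model would achieve.

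The assumed link between load and dropout has some support in Section 2.1.6. In the investigators' earlier chemotherapy trial, seven patients left within a month for progression or toxicity, and a median 190-fold rise in viral RNA coincided with progression. The regimen was different, so neither the rate nor the size need carry over.

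**The case against.** The strongest reply is that the plan says analysis of variance *methods*, a generic term that can include a repeated-measures or random-patient-effect form. A reader might infer that the estimate is bound to be imprecise or confined to survivors. The text does not support that: it does not say which form will be used, so the defect is a model left open, with weak versions permitted.

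A reader might also take the 3-6 month medians and conclude that 27-47% of acute and lymphoma patients would be dead by week 12 and so lost. That does not hold as a trial figure. No viral-load draw falls at week 12. Section 3.1 requires a life expectancy above 12 weeks and performance status 0-2. It also admits chronic and smoldering disease, and the subtype mix is not stated.

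Two design features limit the problem. The week 4 and week 8 draws precede the first scheduled response evaluation, and an end-of-treatment sample is planned, so a patient who stops can still contribute a later value. Both points stand, and they confine the concern mainly to the draws from week 20 on. They do not remove it. Patients can stop before week 8, some may die without a final sample, and that sample falls at a different time in each patient with no stated place in a time factor.

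A step from baseline to on-treatment can be separated from a trend across on-treatment visits. That is correct, but both are within-patient time effects.

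Finally, Section 13.3 calls the analysis descriptive, and viral load drives no stopping or efficacy decision. That lowers the stakes, but a descriptive estimate can still be biased by selection.

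**Conclusion.** The point holds in a limited form. It is certain from the documents that there is no between-patient treatment factor, that the samples are repeated within patient, and that no model or missing-data rule covers this.

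The consequences are conditional. If pairing is ignored, the standard error of change is inflated 1.4 to 2.2 times for ρ of 0.5 to 0.8. If completers only, or whoever remains at each visit, are analysed, the later estimates may lean toward an apparent fall. That direction rests on rising load going with dropout. The simulated sizes are illustrations, because the plan gives no SD, correlation or dropout rate.

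A better model does not cure small numbers: with 20 patients, or 9, the late estimates stay wide. It also rests on missing at random and does not resolve truncation by death. This is worth correcting before the data are examined, as a secondary-analysis matter. The primary response design is not affected.

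**What to change.** In Section 13.3, replace the ANOVA sentence with a specification along these lines:

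- Drop the treatment factor. The estimand is within-patient change from baseline.
- Fit a linear mixed model, separately for log-transformed DNA load and log-transformed RNA ratio, with a stated rule for zero values. The existing log base 2 step covers DNA only, so the RNA scale must be added.
- Include a random patient effect and use all available samples.
- Treat baseline, Cycle 3 Day 1 and Cycle 5 Day 1 as categorical visits. Pool the later 12-weekly visits or model them as continuous time. About 23 months of treatment gives roughly ten scheduled draws, too many for separate late-visit effects in 20 patients.
- Name change from baseline at Cycle 5 Day 1 as the main contrast and report it with its interval.
- Enter end-of-treatment samples at their actual time.
- State that the model assumes missing at random and does not address truncation by death, and report the number sampled at each visit.

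The cost is a few sentences and slightly more modelling work. No new data or patients are needed.
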